11.1.2 Disease Parameters

Measurable disease. Measurable lesions are defined as those that can be accurately measured in at least one dimension (longest diameter to be recorded) as ≥ 20 mm with conventional techniques (CT, MRI, x-ray) or as ≥ 10 mm with spiral CT scan. All tumor measurements must be recorded in millimeters (or decimal fractions of centimeters).

Note: Tumor lesions that are situated in a previously irradiated area will not be considered measurable.

Non-measurable disease. All other lesions (or sites of disease), including small lesions (longest diameter <20 mm with conventional techniques or <10 mm using spiral CT scan), are considered non-measurable disease. Bone lesions, leptomeningeal disease, ascites, pleural/pericardial effusions, lymphangitis cutis/pulmonis, inflammatory breast disease, abdominal masses (not followed by CT or MRI), and cystic lesions are all non-measurable.

Target lesions. All measurable lesions up to a maximum of 5 lesions per organ and 10 lesions in total, representative of all involved organs, should be identified as **target lesions** and recorded and measured at baseline. Target lesions should be selected on the basis of their size (lesions with the longest diameter) and their suitability for accurate repeated measurements (either by imaging techniques or clinically). A sum of the longest diameter (LD) for all target lesions will be calculated and reported as the baseline sum LD. The baseline sum LD will be used as reference by which to characterize the objective tumor response.

Non-target lesions. All other lesions (or sites of disease) including any measurable lesions over and above the 10 target lesions should be identified as **non-target lesions** and should also be recorded at baseline. Measurements of these lesions are not required, but the presence or absence of each should be noted throughout follow-up.

11.1.3 Methods for Evaluation of Measurable Disease

All measurements should be taken and recorded in metric notation using a ruler or calipers. All baseline evaluations should be performed as closely as possible to the beginning of treatment and never more than 4 weeks before the beginning of the treatment.

The same method of assessment and the same technique should be used to characterize each identified and reported lesion at baseline and during follow-up. Imaging-based evaluation is preferred to evaluation by clinical examination when both methods have been used to assess the antitumor effect of a treatment.

Clinical lesions Clinical lesions will only be considered measurable when they are superficial (e.g., skin nodules and palpable lymph nodes). In the case of skin lesions, documentation by color photography, including a ruler to estimate the size of the lesion, is recommended.

Chest x-ray Lesions on chest x-ray are acceptable as measurable lesions when they are clearly defined and surrounded by aerated lung. However, CT is preferable.

Conventional CT and MRI These techniques should be performed with cuts of 10 mm or less in slice thickness contiguously. Spiral CT should be performed using a 5 mm contiguous reconstruction algorithm. This applies to tumors of the chest, abdomen, and pelvis. Head and neck tumors and those of extremities usually require specific protocols.

Ultrasound (US) When the primary endpoint of the study is objective response evaluation, US should not be used to measure tumor lesions. It is, however, a possible alternative to clinical measurements of superficial palpable lymph nodes and subcutaneous lesions. US might also be useful to confirm the complete disappearance of superficial lesions usually assessed by clinical examination.

Endoscopy, Laparoscopy The utilization of these techniques for objective tumor evaluation has not yet been fully and widely validated. Their uses in this specific context require sophisticated equipment and a high level of expertise that may only be available in some centers. Therefore, the utilization of such techniques for objective tumor response should be restricted to validation purposes in reference centers. However, such techniques may be useful to confirm complete pathological response when biopsies are obtained.

Tumor markers Tumor markers alone cannot be used to assess response. If markers are initially above the upper normal limit, they must normalize for a patient to be considered in complete clinical response.

Cytology, Histology These techniques can be used to differentiate between partial responses (PR) and complete responses (CR) in rare cases (e.g., residual lesions in tumor types, such as germ cell tumors, where known residual benign tumors can remain).

The cytological confirmation of the neoplastic origin of any effusion that appears or worsens during treatment when the measurable tumor has met criteria for response or stable disease is mandatory to differentiate between response or stable disease (an effusion may be a side effect of the treatment) and progressive disease.

11.1.4 Response Criteria

11.1.4.1 Evaluation of Target Lesions

Complete Response (CR):	Disappearance of all target lesions.
Partial Response (PR):	At least a 30% decrease in the sum of the longest diameter (LD) of target lesions, taking as reference the baseline sum LD.
Progressive Disease (PD):	At least a 20% increase in the sum of the LD of target lesions, taking as reference the smallest sum LD recorded since the treatment started or the appearance of one or more new lesions.
Stable Disease (SD):	Neither sufficient shrinkage to qualify for PR nor sufficient increase to qualify for PD, taking as reference the smallest sum LD since the treatment started.

11.1.4.2 Evaluation of Non-Target Lesions

Complete Response (CR):	Disappearance of all non-target lesions and normalization of tumor marker level.
Stable Disease (SD) :	Persistence of one or more non-target lesion(s) and/or maintenance of tumor marker level above the normal limits.
Progressive Disease (PD):	Appearance of one or more new lesions and/or unequivocal progression of existing non-target lesions.

Although a clear progression of "non-target" lesions only is exceptional, the opinion of the treating physician should prevail in such circumstances, and the progression status should be confirmed at a later time by the review panel (or Principal Investigator).

11.1.4.3 Evaluation of Best Overall Response

The best overall response is the best response recorded from the start of the treatment until disease progression/recurrence (taking as reference for progressive disease the smallest measurements recorded since the treatment started). The patient's best response assignment will depend on the achievement of both measurement and confirmation criteria at least 4 weeks after initial response is documented.

Target	Non-Target	New	Overall	Best Response for this
Lesions	Lesions	Lesions	Response	Category Also Requires:
CR	CR	No	CR	\geq 4 wks. confirmation
CR	Non-CR/Non-	No	PR	
	PD			\geq 4 wks. confirmation
PR	Non-PD	No	PR	
SD	Non-PD	No	SD	documented at least once ≥ 4
				wks. from baseline
PD	Any	Yes or No	PD	
Any	PD*	Yes or No	PD	no prior SD, PR or CR
Any	Any	Yes	PD	
* In excepti	onal circumstances	, unequivocal p	progression in	non-target lesions may be
accepted a	as disease progressi	on.		

Note: Patients with a global deterioration of health status requiring discontinuation of treatment without objective evidence of disease progression at that time should be reported as "*symptomatic deterioration*." Every effort should be made to document the objective progression even after discontinuation of treatment.

11.1.5 **Duration of Response**

Duration of overall response: The duration of overall response is measured from the time measurement criteria are met for CR or PR (whichever is first recorded) until the first date that recurrent or progressive disease is objectively documented (taking as reference for progressive disease the smallest measurements recorded since the treatment started).

The duration of overall CR is measured from the time measurement criteria are first met for CR until the first date that recurrent disease is objectively documented.

Duration of stable disease: Stable disease is measured from the start of the treatment until the criteria for progression are met, taking as reference the smallest measurements recorded since the treatment started.

11.1.6 Progression-free survival:

Progression-free survival (PFS) will be defined as time from first dose of capecitabine to time to clinical or imaging evidence of progressive disease.

11.1.7 **Response Review**

The imaging for any subjects obtaining a CR or PR will be reviewed centrally at the University of Wisconsin by an independent investigator.

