1. OBJECTIVES

1.1. **Primary Objective**: To characterize the effect on pharmacokinetic parameters of capecitabine, when dosed using actual versus ideal body weight in obese patients with advanced solid tumors.

1.2. Secondary Objectives:

1.2.1 To characterize the response rate and progression free survival with capecitabine therapy in obese subjects with advanced solid tumors

1.2.2 To determine capecitabine pharmacokinetics in obese patients compared with normal weight historical controls.

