Diarrhea: Patients should be instructed prior to cycle 1, day 1 in the proper use of antidiarrhea agents (such as loperamide [Imodium AD]). For example, with loperamide [Imodium AD], instruct patients to take 4 mg (2 capsules) after the first loose stool of the day, and 2 mg each loose stool thereafter. 4 mg may be taken every 4 hours overnight. Instruct the patient to stop taking the Imodium when they have not had a bowel movement for 12 hours. Total daily dose should not exceed 16 mg. Patients should be instructed to call for any diarrhea not improved by Imodium.

5.3 **Duration of Therapy**

In the absence of treatment delays due to adverse event(s), treatment may continue until one of the following criteria applies:

- Disease progression.
- Intercurrent illness that prevents further administration of treatment.
- Unacceptable adverse event(s).
- Patient decides to withdraw from the study or is unevaluable after cycle 1.
- General or specific changes in the patient's condition render the patient unacceptable for further treatment in the judgment of the investigator.
- Treatment delay greater than 2 weeks

5.4 **Duration of Follow Up**

All patients enrolled in the study will be followed until both of the following criteria are met:

1. Study drug is discontinued (for any reason)

2 All study drug related adverse events have either resolved to grade 1 or stable per the discretion of the treating physician.

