5.5 Criteria for Removal from Study

Patients will be removed from study when any of the criteria listed in Section 5.3 applies. The reason for study removal and the date the patient was removed must be documented in the Case Report Form.

5.6 **Definition of Evaluable Patients**

Patients will be evaluable for the primary endpoint if he or she takes 100% of their capecitabine dose days 1 through 9 and at least 90% of their capecitabine dose days 10 through 15 in cycle one. Unevaluable patients will go off study after cycle 1, but may continue to be treated with commercial capecitabine per the discretion of the treating physician.

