13.4 Analysis of Secondary Endpoints

Responses will be determined using RECIST as described in Section12 and summarized in tabular format. The complete and partial response rates will be calculated and reported along with the corresponding 95% confidence intervals. All eligible subjects (intent-to-treat population) will be included in the calculation of the response rate. Progression-free survival will be analyzed using the Kaplan-Meier method.

PK parameters (based on ideal body weight and actual body weight) of the study participants will be summarized using standard descriptive statistics in terms means, standard deviations and ranges. A two-sample t-test will be used to compare the mean values in the PK parameters in obese patients with normal weight historical controls.

13.5 **Reporting and Exclusions**

13.5.1 **Evaluation of toxicity.** All patients will be evaluable for toxicity from the time of their first treatment with capecitabine.

13.5.2 **Evaluation of response.** All patients included in the study must be assessed for response to treatment, even if there are major protocol treatment deviations or if they are ineligible. Each patient will be assigned one of the following categories: 1) complete response, 2) partial response, 3) stable disease, 4) progressive disease, 5) early death from malignant disease, 6) early death from toxicity, 7) early death because of other cause, or 9) unknown (not assessable due to measurable disease only or insufficient data). [Note: By arbitrary convention, category 9 usually designates the "unknown" status of any type of data in a clinical database.]

All of the patients who met the eligibility criteria (with the possible exception of those who received no study medication) should be included in the main analysis of the response rate. Patients in response categories 4-9 should be considered to have a treatment failure (disease progression). Thus, an incorrect treatment schedule or drug administration does not result in exclusion from the analysis of the response rate.

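### PFS is defined by progression alone, with no place for death and no censoring rule, so the endpoint as written is time to progression under a PFS label

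*Combined protocol and SAP*

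**What the plan says.** PFS appears in four places in the combined protocol and SAP.

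- Section 1.2.1 makes it a secondary objective: "To characterize the response rate and progression free survival with capecitabine therapy in obese subjects with advanced solid tumors". Section 13.1 lists it as a secondary endpoint.
- Section 11.1.6 defines it as "time from first dose of capecitabine to time to clinical or imaging evidence of progressive disease".
- Section 13.4 gives the analysis in one sentence: "Progression-free survival will be analyzed using the Kaplan-Meier method".

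Section 13.5.2 is the nearest text on death. Its response categories 5 to 7 are early deaths from the cancer, from toxicity and from other causes. It says "Patients in response categories 4-9 should be considered to have a treatment failure", and adds in parentheses that such failure means disease progression.

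On leaving the study, section 5.5 says "Patients will be removed from study when any of the criteria listed in Section 5.3 applies". Those criteria include reasons other than progression, among them "Patient decides to withdraw from the study or is unevaluable after cycle 1". Section 5.6 adds that "Unevaluable patients will go off study after cycle 1". Section 5.4 ends follow-up once the drug has been stopped and drug-related adverse events have resolved or stabilised. It does not mention progression or survival.

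**The concern.** A Kaplan-Meier analysis needs two rules: what counts as an event, and when a patient without an event is censored. Section 11.1.6 gives the first and names progression only. The second appears nowhere. Followed literally, the plan estimates time to progression, while a reader of the report will take PFS to include death.

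The patients affected are those who die with no earlier progression on record. Because 11.1.6 accepts clinical evidence of progression, many cancer deaths may already be captured. What remains would mainly be deaths from toxicity, from other causes, or of sudden onset. If an analyst censored them, the curve would look better than true PFS. Two analysts could also produce different curves from the same data, one applying 11.1.6 literally and the other borrowing the failure rule in 13.5.2.

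**Working it through.** The documents state no PFS figure (no expected median, event count or power), so there is nothing to reproduce. The check sets the passages side by side and then shows the direction and possible size of the effect.

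**1. Can a death be placed as a PFS event?**

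- 11.1.6: the clock starts at first dose, the event is progression, and death is absent.
- 13.4: the method only.
- 13.5.2: deaths count as failures, but under evaluation of response and for the response rate. It covers only early deaths without defining early, gives no event date and does not refer to 11.1.6. Category 9 (unknown) is also a failure there, and that cannot be carried into a time-to-event analysis without a date.

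An early toxic death is therefore a failure for response but not a named event for PFS.

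**2. Direction and size if such deaths are censored.** Let f be the share of first events that are deaths without progression. The documents do not give f, so 0 to 30% is an assumption. With constant total hazard L, median PFS is ln 2 / L. With those deaths censored the hazard is (1-f)L, so:

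- median ratio = 1/(1-f)
- estimate at the true PFS median = 0.5^(1-f)
- chance that at least one of the first five of ten events is such a death, with no other censoring = 1-(1-f)^5

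| f | Median ratio | Estimate at true median | Chance in first five events |
|---|---|---|---|
| 0% | 1.00 | 0.500 | 0% |
| 5% | 1.05 | 0.518 | 23% |
| 10% | 1.11 | 0.536 | 41% |
| 20% | 1.25 | 0.574 | 67% |
| 30% | 1.43 | 0.616 | 83% |

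**3. Ten-patient illustration (invented data).** First events fall at months 1 to 10, and the median is the first month at which the curve is at or below 0.5.

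- All counted as events: S(5) = 0.50, median 5.
- One death censored in months 1 to 5: S(5) runs from 5/9 = 0.556 (month 1) to 0.600 (month 5), median 6.
- One death censored in months 6 to 10: S(5) = 0.50, median 5. Half of the ten placements change nothing.
- Two deaths censored, at months 2 and 4: S(5) = 0.9 x 7/8 x 5/6 = 0.656, median 7. Over all 45 pairs the median is 5 in 10, 6 in 21 and 7 in 14.

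These counts depend on the convention. With a midpoint median the baseline is 5.5 and a death censored at month 6 also moves the median to 6, so six of ten placements shift it.

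**4. Against sampling error.** The interval from the 2nd to the 9th of ten ordered times covers the median with probability 1 - 2 x P(Bin(10, 0.5) <= 1) = 1 - 2 x 11/1024 = 0.979. Here that is month 2 to month 9. A shift from 5 to 6 or 7 lies well inside it.

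**The case against.** The strongest reply is that 13.5.2 already equates early death with disease progression, which is the event in 11.1.6, so the documents are ambiguous rather than wrong. This stands in part. The plan never says that deaths will be censored, and a reader who infers that it does goes beyond the text. But a rule written for the response rate, limited to an undefined early period and without a date, cannot supply a PFS event. It is a conflict to be reconciled.

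A reader might also infer that progression and death would go largely unobserved, so that the study needs longer follow-up. The documents do not support that.

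- Section 11.1 fixes one re-evaluation at 6 to 9 weeks and leaves later ones to the treating physician. But the study calendar lists tumor measurements every 2 to 3 cycles and again at off study, and section 6.1 requires absence of progression on Day 1 of each further cycle.
- The expedited-reporting table in section 7.3 covers every death within 30 days of the last dose, whatever its attribution. Many toxic or sudden deaths would fall in that window, so their dates would be available.
- Extended follow-up for progression in a pharmacokinetic pilot is a design preference.

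Finally, one could argue that a descriptive endpoint in about 10 patients does not merit the point. That limits its weight. It does not make the label correct.

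**Conclusion.** The point holds as a mismatch between definition and label. Progression is the only PFS event, no censoring rule exists, and 13.5.2 pulls in another direction. Confidence in that textual conclusion is high.

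The size is not established. Any bias would be favourable if deaths without progression were censored. The range of 1.00 to 1.43 for the median rests on an assumed f of 0 to 30% and constant hazards, and the lower end may be nearer because clinical progression counts. A reader might infer that the reported PFS will be materially inflated. The documents do not support this: they give no f, and in about 10 patients the shift lies within sampling error.

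The consequence is limited. PFS is secondary and descriptive, no hypothesis or decision depends on it, and the study is sized on AUC and Cmax, so the primary analysis and n=10 do not change. The change should still be made, because it is cheap and the figure would otherwise not be what its name says.

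**What to change.** - In 11.1.6 and 13.4, define PFS as the time from first dose to progression or death from any cause, whichever comes first. Censor patients who are alive and progression-free at their last disease assessment.
- Reconcile 13.5.2 with this, so that a death is handled consistently for response and for PFS.
- State that patients who leave the study without progression, including those unevaluable for pharmacokinetics who go off study after cycle 1, are censored at their last or off-study assessment. Report how many there are.
- If the sponsor prefers to keep the present event definition, rename the endpoint time to progression throughout, including objective 1.2.1, and state how deaths are handled.

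Collecting later progression or death dates from routine records is optional. If it is done, 5.4 to 5.6 need a matching line.

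The cost is a few sentences and a PFS figure that may look slightly less favourable. Optional chart review would cover the 10 evaluable patients and any unevaluable patients whom they replaced. Sample size and the pharmacokinetic analysis do not change.

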12. DATA REPORTING / REGULATORY CONSIDERATIONS

Guidelines and instructions for AE reporting can be found in Section 7.0 (Adverse Event Reporting Requirements).

Study sites are responsible for entering case report forms directly into the Oncore database in accordance with the UWCCC data management policy. Data must be submitted within 2 weeks of a subject visit and will be monitored monthly by the Phase I Cancer Research office at the UWCCC.

13. STATISTICAL CONSIDERATIONS

13.1 Study Design/Endpoints

The primary endpoints are the PK parameters (AUC and Cmax) of capecitabine when dosed using actual versus ideal body weight. Secondary endpoints are response and progression-free survival.

A single arm study design will be used to characterize the effect on pharmacokinetic parameters of capecitabine, when dosed using actual versus ideal body weight. Ideal body with based dosing of capecitabine when be used for cycle 1 from day 1 to day 7 followed by an actual body weight based dosing from Day 9 to Day 15. There will be a wash-out period on Day 8.

PK parameters will be summarized in terms of number of observations, means, standard deviations, medians, and ranges, stratified by assessment time point. The noncompartmental method will be used to estimate PK parameters. AUC will be estimated using the Lagrange approximation method. A paired t-test will be used to compare the PK parameters between the full weight and limited weight based dosing. If the PK parameters are not normally distributed, then an appropriate transformation will be identified before conducting the comparison. The comparison of AUC and Cmax between full weight and limited based dosing will be also performed using a population pharmacokinetics analysis, based on a nonlinear mixed effects modeling approach.

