(http://www.fda.gov/Drugs/DevelopmentApprovalProcess/DevelopmentResources/DrugInter actionsLabeling/ucm093664.htm) capecitabine is a weak inhibitor of CYP2C9. Thus, based on the drug interaction table in Appendix C, no medications would be contraindicated.

2.4 Hypothesis: Our hypothesis is that use of full weight based chemotherapy dosing will be associated with a significantly higher AUC and Cmax. The results of this study will advance oncologists' understanding of the potential impact of using limited weight-based dosing for capecitabine and provide preliminary data to demonstrate the need evaluate the importance of weight-based dosing for other chemotherapy and targeted agents.

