13.2 Sample Size/Accrual Rate

The primary objective is to characterize the effect on pharmacokinetic parameters when capecitabine is dosed on actual versus ideal body weight results in obese patients with advanced solid tumors. A mean difference in the AUC and Cmax of at least 30% between the ideal body weight dosing versus the actual body with based dosing will be considered as a minimal important difference. Based on the results of several previous PK studies involving capecitabine, it is anticipated that the overall standard deviation for the difference between the two dosing strategies is at most 25% of the mean difference. The following table shows the required sample sizes to detect various mean differences in PK parameters between the two dosing strategies at the two-sided 0.025 (=0.05/2 - a Bonferroni adjustment for comparing both AUC and Cmax) significance level with 80%

power, assuming a standard deviation ranging from 20-30%.

with 0070	power ai me inc	biaca 0.025 sig	infleance level				
	Mean difference in PK parameters between the ideal versus actual weight based dosing strategy						
Standard	20%	25%	30%	35%	40%		
Deviation							
20%	13	9	7	6	6		
25%	18	13	10	8	7		
30%	24	17	13	10	9		

Table 13.1: *Required sample sizes to detect various mean differences in PK parameters with 80% power at the two-sided 0.025 significance level*

A sample size of n=10 patients is proposed for this study. With a sample size of 10 patients, a clinically important difference of 30% between the ideal and actual body weight based dosing will be detected with 82% power at the one-sided 0.025 (=0.05/2 - a Bonferroni adjustment for evaluating both AUC and Cmax) significance level, assuming an overall standard deviation of 25%. A mean difference of only 25% will be detected with 68% power. Patients will be evaluable for the primary endpoint if he or she completes cycle 1, capecitabine therapy without dose reduction or skipped doses. Any patient who does not meet these criteria will be replaced.

The anticipated accrual is 1-2 patients per month. Therefore, the study is expected to be completed within 6-12 months after first accrual.

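### Does the fixed dosing order, with 5-FU exposure rising over time, undermine the day 9 versus day 1 comparison?

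*Combined protocol and SAP*

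**What the plan says.** Section 13.1 describes one arm and one sequence. Ideal-weight dosing is "used for cycle 1 from day 1 to day 7 followed by an actual body weight based dosing from Day 9 to Day 15". It adds: "There will be a wash-out period on Day 8". Section 9.1 and the sampling table in 9.2 give seven-point profiles on days 1 and 9, and a single pre-dose sample on days 7 and 15.

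On the endpoint, 13.1 states: "The primary endpoints are the PK parameters (AUC and Cmax) of capecitabine". On the test: "A paired t-test will be used to compare the PK parameters between the full weight and limited weight based dosing". Section 13.2 divides 0.05 by two as "a Bonferroni adjustment for comparing both AUC and Cmax", and says that a mean difference of at least 30% "will be considered as a minimal important difference". The primary objective (1.1) is also worded for capecitabine: "To characterize the effect on pharmacokinetic parameters of capecitabine, when dosed using actual versus ideal body weight".

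Section 9.1 measures 5-FU, DFCR and DFUR in the same samples and lists them as metabolites, separately from capecitabine. Section 2.3 reports that capecitabine and 5'-DFCR are dose proportional and stable over time. It reports that AUCs of 5'-DFUR and 5-FU rise more than proportionally with dose, and that 5-FU AUC on day 14 exceeds day 1 by 34%.

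**The concern.** With one sequence, the dosing weight and the day of treatment change together. For an analyte whose exposure drifts with repeated dosing, the paired difference estimates dose effect and drift combined, and neither the paired t-test nor the population model in 13.1 can separate them from these data alone. Section 2.3 says 5-FU is such an analyte.

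The wording leaves some room for this to matter. The paired-test sentence and the hypothesis in 2.4, that "use of full weight based chemotherapy dosing will be associated with a significantly higher AUC and Cmax", name no analyte. The rationale in 2.3 leans on fluorouracil exposure, so readers will want the 5-FU result. If the paired test were run on 5-FU and read as a weight effect, any upward drift would push the estimate in the direction of the hypothesis and could help carry it past the 30% threshold.

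**Working it through.** **1. The plan's own figure.** Inputs from 13.2: n = 10, difference 30%, SD 25%, two-sided 0.025. For a paired t-test the noncentrality is (30/25) × √10 = 3.79, and the critical value on 9 df at 0.0125 per tail is 2.685. Power is 84.2% (stated: 82%). For a 25% difference, noncentrality is 3.16 and power is 68.2% (stated: 68%). Two-sided 0.025 also reproduces all 15 cells of Table 13.1. The text beside these power figures says one-sided, which would give 92.0% and 80.3%; that is a separate matter. The design figures are therefore those of two tests, AUC and Cmax. Testing both parameters for 5-FU as well would need four tests at 0.0125, and power for 30% would fall to 73.5%. The sample size was built for one analyte.

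**2. Carry-over across day 8.** There is no dose on day 8, so at least 24 h separate the last ideal-weight dose from the day 9 dose. With a half-life of about 0.75 h (2.3), that is 24/0.75 = 32 half-lives. Residual drug is not the issue; only a change in 5-FU handling with repeated dosing could be.

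**3. Could the day 7 and 15 samples separate dose from time?** They are pre-dose, at least 10 h after the previous dose (5.1). The 5-FU peak is at about 2 h plus a 1.5 h food delay, 3.5 h in all. The remaining 6.5 h is 6.5/0.75 = 8.7 half-lives, leaving about 0.25% of peak. They cannot.

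**4. How large could the mixing be for 5-FU AUC?** By the formulas in 5.1, dose ratio = √(actual weight / ideal weight). Heights are assumed; BMI 30 is the eligibility minimum (3.1.3).

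- Man, 185 cm: 30 × 1.85² = 102.7 kg actual, 79.5 kg ideal; ratio 1.136.
- Woman, 155 cm: 72.1 kg actual, 47.9 kg ideal; ratio 1.227.

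Take 5-FU as proportional to dose (a floor, since 2.3 says more than proportional), so that observed ratio = dose ratio × time factor.

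| Assumed time factor at day 9 | Ratio 1.136 reads as | Ratio 1.227 reads as |
|---|---|---|
| 1.00 (no drift) | 1.14 | 1.23 |
| 1.21 (linear: 1 + 0.34 × 8/13) | 1.37 | 1.48 |
| 1.34 (day 14 figure) | 1.52 | 1.64 |

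A time factor of 1.30/1.227 = 1.06 to 1.30/1.136 = 1.14 would carry the ratio to 1.30. With no dose effect at all, a 34% drift would be significant at n = 10 with probability 92% at SD 25%, and a 21% drift with probability 51%. At an assumed SD of 85%, the 34% drift gives 13%. So the mixing could be substantial for 5-FU, but no row of the table is established: the documents give no day 9 value and nothing on the effect of the day 8 break.

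**5. Does it reach the planned test?** Four places, read together:

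- 13.1 attaches AUC and Cmax to capecitabine, and the test sentence then refers back to the PK parameters just defined.
- 9.1 and 2.3 both use capecitabine as distinct from its metabolites.
- 13.2 splits alpha over two tests.
- 2.3 gives the parent no change over time across 500 to 3500 mg/m²/day. The planned 2 × 1,250 = 2,500 mg/m²/day is inside that range. The ideal-weight dose per unit of actual surface area is too: 2,500/1.227 = 2,037 for the shorter patient above.

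On the protocol's own statement the time factor for the tested analyte is 1.00.

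**The case for a change.** The strongest case for a change is that section 13 never says what will be done with 5-FU, DFCR and DFUR, although they are measured on the same days and 5-FU motivates the study. Section 9.1 groups all four analytes under one capecitabine heading, so a reader could take the capecitabine PK parameters in 13.1 to include the metabolites. A few words would close that off at no cost to patients, samples or alpha.

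Part of this stands. The role of the metabolites is unstated, and for 5-FU AUC the dosing weight and time are fully aliased. But no section plans a 5-FU paired test or a weight claim from 5-FU, and the 30% threshold is set for the two primary parameters. An unplanned test that someone might run is not a defect in the planned one. Section 13.1 already summarises PK parameters by assessment time point, so the day 1 and day 9 values will be shown as such, and the drift that calls for caution is reported in the same protocol. Dividing the 5-FU ratio by an assumed factor between 1.00 and 1.34 would add a band that rests on no day 9 evidence.

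**Conclusion.** No change is needed. The comparison of AUC and Cmax of parent capecitabine on day 9 and day 1 is not shown to be biased by the fixed order. This rests on two things: reading 13.1 as referring to the parent drug, which the endpoint wording, the two-test alpha split and the terminology of 9.1 all support; and the statement in 2.3 that the parent does not change over time, for which the documents give no figures specific to obese patients.

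The aliasing for 5-FU AUC is real. It may inflate an apparent weight effect by a factor between 1.00 and 1.34, if drift at day 9 does not exceed that at day 14. No time effect is given for 5-FU Cmax or for DFUR. The unstated role of the metabolites is a gap that analysts fill sensibly in a 10-patient pilot meant to characterise pharmacokinetics: report them descriptively, and read 5-FU on day 9 against day 1 as dose and time together. The primary analysis, its alpha and its sample size stay as they are.
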